9.4.2 Safety analyses

Adverse events (AEs) will be listed and tabulated for patients on treatment. AEs will be classified based on the likelihood that they are treatment-related. NCI toxicity Grade 3 and Grade 4 laboratory abnormalities will also be listed.

9.4.3 Other analyses

Exploratory endpoints:

Genetic markers will be plotted using heat-maps and statistically compared across responders and non-responders using the Benjamini-Hochberg correction for multiplicity of p-values.

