8.1 Efficacy assessments

This study will evaluate the primary endpoint of overall response rate by RECIST v1.1. The overall response rate will be calculated by the sponsor (Yale School of Medicine) as the proportion of patients that receive either a partial response or complete response by RECIST v1.1 (*Eur J Ca* 45: 228-247, 2009).

Response Criteria:

Complete Response: Disappearance of all target lesions. Any pathological lymph nodes (whether target or non-target) must have reduction in short axis to <10 mm (<1 cm).

Partial Response: At least a 30% decrease in the sum of the diameters of target lesions, taking as reference the baseline sum diameters.

Progressive Disease: At least a 20% increase in the sum of the diameters of target lesions, taking as reference the smallest sum on study (this includes the baseline sum if that is the smallest on study). In addition to the relative increase of 20%, the sum must also demonstrate an absolute increase of at least 5 mm (0.5 cm). (Note: the appearance of one or more new lesions is also considered progression).

Stable Disease: Neither sufficient shrinkage to qualify as partial response nor sufficient increase to qualify for progressive disease, taking as reference the smallest sum diameters while on study.

Progression-free survival, overall survival and safety are secondary endpoints

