9. STATISTICAL CONSIDERATIONS

9.1 Statistical hypotheses

The primary objective of this study is to assess the efficacy of temozolomide in combination with olaparib in subjects with MGMT promoter hypermethylated advanced colorectal cancer who have progressed on at least one line of systemic chemotherapy by overall response rate as assessed per RECIST v.1.1. We hypothesize that the underlying response rate to the combination therapy is 25% or greater (H_1) compared to a null hypothesis of 5% (H_0) based on historical controls.

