9.2 Sample size determination

The sample size estimation for the single-arm of this phase II study is based on the primary endpoint of objective response rate (ORR). The protocol plans to enroll a total of 30 evaluable patients at the recommended dose level in a single-arm open label phase 2 study Simon's Two-Stage optimal design. There will be screening for eligibility and we will examine several secondary endpoints. Patients will be considered evaluable for the primary endpoint if they complete at least 1 cycle of study treatment followed by response assessment imaging. Patients that are not evaluable may be replaced to ensure the appropriate number of evaluable patients is enrolled as outlined in the sample size determination for the primary endpoint in the Simon's two-stage optimal design described below.

Screen: To be eligible for this trial, patients will first need to be screened for the MGMT promoter hypermethylation and/or MGMT lack of expression. We anticipate at least 20% of those screened will exhibit an appropriate biomarker as well as meet eligibility criteria. To obtain 30 eligible patients, the mean number of patients to be screened is 150. Using the negative binomial distribution as reference, there is a 6% probability more than 190 subjects will need to be screened to attain the 30 eligible patients.

The **primary endpoint** is the objective response rate to the combined therapy and will be assessed in a Simon's two-stage optimal design. Published, historical records anticipate a response rate of 5% or lower and we will assume a null hypothesis of 5%. We will reject this null hypothesis in favor of a higher rate if we observe 4 or more responses in the evaluable patient sample of 30. Patients will be considered evaluable for the primary endpoint if they complete at least 1 cycle of study treatment with response assessment imaging. The trial will terminate early if we do not observe 1 or more responses in the first 9 evaluable patients. The probability of 4 or more responses in a sample of 30 has probability .049, which is the significance level. If the true, underlying response rate is 25% or greater, then this trial has power 90%. The expected sample size is 17 under the null hypothesis. There is a 63% chance of stopping early under the null hypothesis.

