9.4.1 Efficacy analyses

Primary Endpoint: Overall response rate (ORR) by RECIST v1.1 criteria for combined therapy of olaparib and temozolomide.

Analytic Plan for Primary Endpoint:

The objective response is defined as a complete or partial response, as determined by investigator assessment using RECIST v 1.1 and confirmed by repeated assessment > 4 weeks after initial documentation. Patients with missing or no response assessments are classified as non-responders. The trial will terminate early if we do not observe 1 or more responses in the first 9 evaluable patients. The ORR will be estimated using the 95% confidence interval (CI) based on Wilson's method. A 5% 2-sided alpha will be used.

Secondary Endpoints: PFS, OS, Safety

Analysis Plans for Secondary Endpoints:

Secondary endpoints include overall survival, progression-free survival, and toxicity. Survival endpoints will be plotted using the Kaplan-Meier, product-limit method and compared across clinical measurements using Cox proportional hazards regression. Time to progression begins at the time of initial treatment and ends at the earliest of withdrawal, diagnosed progression, or death. For PFS subjects who are alive and have not progressed will be censored at the date of

their last RECIST tumor assessment. For OS subjects who are alive will be censored at the date of their last survival assessment. Toxicity rates will be compared to established rates for these treatments and summarized using means and 95% confidence intervals.

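### The one marker test that section 9.4.3 specifies rests on a handful of responders; adding a rank correlation with tumour shrinkage alongside it would use data already collected

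*Combined protocol and SAP*

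**What the plan says.** Section 9.4.3, and the last sentence of the statistical methods in 1.2, give one method for the markers: "Genetic markers will be plotted using heat-maps and statistically compared across responders and non-responders using the Benjamini-Hochberg correction for multiplicity of p-values". No two-group test is named, and percentage change in tumour size is not analysed anywhere in the plan.

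The stated aims are wider than that method. Section 3 and Table 2 in 1.2 list association of γH2AX with response and survival, and of sequencing, methylation and expression profiles with efficacy and clinical parameters. Section 8.8 plans correlation of whole-blood expression with outcome. Section 9.4.1 gives Cox regression for the survival endpoints across clinical measurements but does not mention markers.

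Response is a cut on a continuous quantity. Section 8.1 defines partial response as "At least a 30% decrease in the sum of the diameters of target lesions", relative to baseline. Inclusion criterion 12 requires a measurable lesion, and Table 1 schedules scans about every six weeks. For the primary endpoint, section 9.4.1 adds confirmation more than four weeks later and states: "Patients with missing or no response assessments are classified as non-responders".

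The number of responders follows from the two-stage design in 9.1 and 9.2. The hypothesis is that "the underlying response rate to the combination therapy is 25% or greater", against a null of 5%; success is declared "if we observe 4 or more responses in the evaluable patient sample of 30"; and "The trial will terminate early if we do not observe 1 or more responses in the first 9 evaluable patients".

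**The concern.** Splitting about 30 patients at the 30% shrinkage cut treats a 29% decrease like a 40% increase, and one arm of the comparison may hold only a few patients. With one responder in 30, the smallest possible two-sided exact rank-test p-value is .067, so no marker could reach .05. With no responders the test cannot be run at all.

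The markers are the subject of the exploratory objectives, and patients give a pre-treatment biopsy (where judged safe) and serial research blood for them. If a marker tracks shrinkage along the whole scale, the specified analysis could easily miss it although the sums that would show it are in the database. Turning to those sums only after the data are seen would be a post hoc choice of outcome.

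**Working it through.** **1. The plan's own design figures.** Inputs from 9.1 and 9.2: stop at 0/9; reject at 4 or more of 30; rates 5% and 25%.
- Early stop under the null: 0.95^9 = 0.630 (plan: 63%).
- Expected sample size under the null: 9 + 21 × (1 − 0.630) = 16.8 (plan: 17).
- Exact two-stage binomial, at least 1/9 and at least 4/30: 0.0489 at 5%, which the plan says "has probability .049, which is the significance level"; power 0.902 at 25% (plan: 90%).

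All four reproduce.

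**2. How many responders the marker test would have.** The chance of a 0/9 stop is (1 − p)^9. The other columns condition on passing stage 1.

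| True rate | 0/9 stop | Mean responders | Fewer than 4 | More than 8 |
|---|---|---|---|---|
| 5% | 63% | 2.3 | 87% | 0% |
| 10% | 39% | 3.6 | 52% | 0.3% |
| 25% | 7.5% | 7.7 | 2.5% | 35% |

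Four is the success threshold, and 30 × 0.25 = 7.5 is the unconditional expectation at the target rate. Values from 4 to 8 are therefore a working range for a trial that succeeds near its target, not a prediction interval.

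**3. Smallest attainable p-value.** A two-sided exact rank test with k responders of 30 cannot go below 2/C(30,k): 2/30 = .067 for k = 1 and 2/435 = .0046 for k = 2.

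**4. Information kept by the split.** For a normal outcome cut at share q, the asymptotic relative efficiency is φ(z_q)²/[q(1 − q)].
- 4/30: 0.2153²/0.1156 = 0.40
- 6/30: 0.2800²/0.1600 = 0.49
- 8/30: 0.3286²/0.1956 = 0.55

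Under a graded relation the split discards about 45–60% of the information.

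**5. Power if the relation is graded.** Assumptions: n = 30; marker and tumour change bivariate normal with correlation ρ; responders are the k patients with most shrinkage; Spearman test against exact Wilcoxon. The documents give no marker effect size or marker count, so ρ and the per-marker level are assumed. Simulated power:

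| Level | ρ | Rank correlation | Split, k = 4 / 6 / 8 |
|---|---|---|---|
| .05 | 0.4 | 55% | 23 / 28 / 32% |
| .05 | 0.5 | 77% | 35 / 43 / 49% |
| .05 | 0.6 | 93% | 51 / 62 / 69% |
| .005 | 0.5 | 45% | 9 / 13 / 17% |
| .005 | 0.6 | 71% | 16 / 25 / 32% |

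The .005 rows only illustrate a stricter level. BH has no fixed cut-off.

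**6. Power if the marker differs only in responders.** Same n and tests; marker shifted 1.5 SD in responders and otherwise unrelated to change; level .05. Rank correlation against split: 24% vs 70% (k = 4), 46% vs 85% (k = 6), 68% vs 92% (k = 8). The ordering reverses.

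**7. Limits on the gain.** After a 0/9 stop the rank correlation can still be computed in the nine evaluable patients, but its power at .05 is only 26–53% for ρ from 0.5 to 0.7. Missing biopsies or scans also cost power: the correlation detectable with 80% power at .05 is 0.49 at n = 30 and 0.55 at n = 24.

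**The case against.** The strongest reply is that the graded model decides the answer in advance, since a linear relation across the whole range must favour a continuous test. The protocol's own background points partly the other way: section 2.2 reports that in the temozolomide–irinotecan trial every responder was MGMT-negative on immunohistochemistry. Step 6 shows that for a responder-type marker the split wins clearly. This stands. A reader might infer that the continuous analysis is simply better and should replace the responder test. The documents do not support that, because γH2AX with response is a listed endpoint and the split is the test that matches it.

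Second, best percentage change is not just a finer version of response. It ignores confirmation and new lesions, so a patient with shrinking targets and a new lesion would rank well. Section 9.3 also keeps in the response analysis patients who died or stopped before the first assessment for clinical progression or toxicity, and a careless continuous analysis would drop them. This stands too, and the added analysis needs an explicit ranking rule.

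Third, a reader might infer that markers are to be related to response and nothing else. Sections 3 and 8.8 say otherwise. What is true is that 9.4.3 assigns a method only to the responder comparison.

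Fourth, the analysis is exploratory and the plan claims no power for it. That bears on the priority of the change, not on whether it is worth making.

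**Conclusion.** The point holds as a cheap improvement. The one specified marker test rests on few responders, cannot be run among the nine evaluable patients after a 0/9 stop, and cannot reach .05 with one responder in 30. A rank correlation with best percentage change would raise power at .05 from 35–50% to about 77% for a graded marker, given ρ = 0.5, n = 30 and 4 to 8 responders. For a marker that differs only in responders it would do worse than the split, so the case is for running both.

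Two further readings go beyond the text. The 63% chance of having no responders applies at a true rate of 5%; at the target rate it is 7.5%. And the rule in 9.4.1 that counts missing assessments as non-response is written for the primary endpoint; 9.4.3 does not say that it carries over to the markers.

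The size of the gain rests on assumed correlations, on a graded relation, and on how complete the biopsies and scans are. Table 1 requires the pre-treatment biopsy only where it is judged low-risk and safe, so the marker sample may be below 30.

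**What to change.** In 9.4.3 and 1.2:
- Keep the responder versus non-responder test.
- Add a rank correlation of each marker with best percentage change from baseline in the sum of target diameters.
- Apply BH over both sets of tests together.
- Rank as worst, tied, the patients who progressed at the first scan (including by new lesions), and those who died, progressed, or stopped for clinical progression or toxicity before any post-baseline scan. This is in line with the response set in 9.3. Omit only patients unassessed for other reasons.

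The cost is a few lines of plan text and a little more analysis work. No new data are needed, and the primary test, its significance level and the sample size do not change. The downside is a larger BH family, with two tests per marker, which halves the threshold for the smallest p-value. That does not undo the gain for a graded marker: at ρ = 0.5 the rank correlation has 26% power even at a per-marker level of .001, against 9–17% for the split at .005. For a responder-only marker it is a modest loss.

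The same edit could name a method for the survival associations listed in section 3, which is a separate gap.

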9.4.4 Methods for multiplicity control

This is a single arm study with an integral biomarker therefore no adjustments for multiplicity are planned other than that mentioned in section 9.4.3 for the exploratory endpoints.

9.5 Interim analyses

An interim efficacy analysis will be performed after the first 9 patients are evaluated to determine whether or not to terminate the trial for futility, as noted in section 9.4.

9.5.1 Data monitoring committee (DMC)

The study principal investigator and YCCI are responsible for monitoring the performance of all of the participating investigators. This will be performed by conducting a study site initiation visit as well as regularly scheduled monitoring visits and/or remote monitoring throughout the life of the protocol. At the end of the trial, the monitor will then perform a study site close-out visit.

YCCI will utilize their institution's initiation, monitoring and close-out visit reports. Following each site visit, a visit report will be generated containing information on site activities, and a summary of pertinent points and action items together with a copy of the follow-up letter will be sent to each investigative site.

During these monitoring visits, some of the items that will be reviewed are the following:

- Training of the sites
- Site personnel qualifications to participate in the trial
- That study related documents are current
- That regulatory compliance is accomplished

- That each subject has signed the informed consent
- That the current and approved protocol is complied with (including reporting and logging of all protocol deviations)
- That all SAEs and AEs have been reported to the local regulatory and Ethics/IRB Committees, YCCI and Astra Zeneca, as appropriate
- That source documentation matches CRFs
- That required procedures for study drug accountability, distribution, and storage are followed.

YCCI will document the required study monitoring activities in a Study Monitoring Plan.

9.5.2 Safety Monitoring

The Yale Cancer Center Data and Safety Monitoring Committee (DSMC) will provide the primary oversight of data and safety monitoring. The Yale DSMC will review and monitor compliance, toxicity and deviations from this study. The committee is composed of clinical specialists with experience in oncology and who have no direct relationship with the study. Information that raises any questions about participant safety will be addressed with the Principal Investigator.

The DSMC will review this protocol at a minimum of once every six months. Information to be provided to the committee includes: a study narrative by the PI, a summary DSMC report produced by OnCore (which includes participant accrual, response, trial status history, SAEs, Adverse Events, Deviations and survival); audit results, and monitoring reports as applicable. Other information (e.g. scans, laboratory values) will be provided upon request.

The Yale DSMC will perform an interim safety analysis after 15 patients have received at least 1 cycle (28 days) of treatment to determine whether there are any safety issues and to assess whether it is safe to continue enrollment. Enrollment will be suspended until approval is granted from the DSMC to proceed completion of enrollment.

If a new unexpected toxicity is identified from the above safety review, or if the periodic review of all the adverse events and laboratory data raises safety concerns, it may result in revision of the consent form, amendment of the protocol and/or suspension of the protocol.

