4.2 Safety Evaluation Period

A safety evaluation period to assess for dose limiting toxicity (DLT) will be employed for at least the first 6 treated patients. Should excessive toxicity be observed at the starting dose, a dose de-escalation schema will be used for TMZ to 60 mg/m², while the olaparib will be maintained at the specified dose of 150 mg twice daily. Patients will be enrolled in cohorts of 3 during the safety evaluation period. For the first 3 patients treated on the study with olaparib 150 mg twice daily and TMZ 75 mg/m², if $\leq 1/3$ DLTs are observed, 3 additional patients will be enrolled at this dose and if $\leq 1/6$ DLTs are seen enrolment will proceed at this dose. If 2 or more DLTs are observed in either the first 3 or 6 patients treated at the starting doses, the TMZ dose will be decreased to 60 mg/m² with olaparib 150 mg twice daily. If 2 or more DLTs are seen in either the first 3 or 6 patients treated at TMZ 60 mg/m² with olaparib 150 mg twice daily then a further dose reduction to TMZ 50 mg/m² with olaparib 150 mg twice daily will be done. The doses of TMZ 50 mg/m² D1-7 with olaparib 150 mg twice daily have previously been tested as outlined in section 4.5. Therefore if the starting doses require reduction to TMZ 50 mg/m² D1-7 with olaparib 150 mg twice daily then safety will be assessed per the data safety monitoring plan as outlined in section 9.5.2.

The dose management tables throughout the protocol will be adjusted in an amendment as necessary if an alternate starting dose is identified. If a dose reduction is necessary, at least 9 patients (per early stopping rule) and up to 30 evaluable patients will be treated at the reduced dose as part of the efficacy analysis. Therefore in the case of a dose reduction the enrolment of 30 patients will be maintained at the same dose.

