9.3 Populations for analyses

Table 15.

Outcome variable	Populations
Efficacy Data	
ORR	Efficacy analysis set (ITT population)
PFS	Efficacy analysis set (ITT population)
OS	Efficacy analysis set (ITT population)
Safety Data	
AEs	Safety analysis set
ECOG performance status	Safety analysis set

AE Adverse events; ORR Overall response rate; PFS Progression free survival; OS Overall survival; ECOG Eastern Cooperative Oncology Group; ITT Intention to treat

All Subject Analysis Set

The All Subject Analysis Set will include information from all screened subjects, including those who did not meet the study entry criteria or did not receive a study treatment. This data set will only be used for disposition in which all screened subjects are accounted for.

Efficacy Analysis Set (ITT population)

The Efficacy Analysis Set will include all subjects who receive any amount of study treatment for efficacy analyses. Efficacy analyses will be based on the actual treatment received. The ORR analysis will be based on subjects who are in the Efficacy Analysis Set and who had disease assessment at baseline and at least 1 follow up disease assessment or subjects who died or

stopped treatment before the first scheduled disease assessment due to clinical progression or toxicity.

Safety Analysis Set

The Safety Analysis Set will include data from all subjects who receive any amount of study drug. Safety analysis will be based on the actual treatment received. All data will be included, and no subjects excluded because of protocol violations.

Schedule of Analysis

This is an open-label study. Ongoing analyses to help manage the study and support the DSMC reviews for safety and antitumor activity will be undertaken. A final analysis will be conducted after all subjects have completed the study.

Disposition

The number and percentage (n, %) of subjects enrolled, treated, lost to follow-up, and withdrawn from treatment or discontinued from the study (with reason) will be summarized. The sample sizes for the Efficacy Analysis Set, Safety Analysis Set will be clearly identified. All subjects in the All Subject Analysis Set will be included in the disposition analysis.

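### The one DSMC review with an automatic enrolment hold counts only patients who have received a full cycle, so losses during cycle 1 push it back

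*Combined protocol and SAP*

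**What the plan says.** Section 9.5.2 (Safety Monitoring) sets the trigger: "The Yale DSMC will perform an interim safety analysis after 15 patients have received at least 1 cycle (28 days) of treatment". It attaches a hold: "Enrollment will be suspended until approval is granted from the DSMC to proceed completion of enrollment". No other sentence counts patients who leave before a full cycle, and neither a number treated nor a calendar date can set off this review instead.

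The same section provides a second, recurring review: "The DSMC will review this protocol at a minimum of once every six months". It carries no automatic hold. If that review or the interim one raises concerns, "it may result in revision of the consent form, amendment of the protocol and/or suspension of the protocol".

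Section 4.2 adds an earlier control: "A safety evaluation period to assess for dose limiting toxicity (DLT) will be employed for at least the first 6 treated patients". Patients enter in cohorts of three, and two or more DLTs lower the TMZ dose. If dosing reaches TMZ 50 mg/m², "then safety will be assessed per the data safety monitoring plan as outlined in section 9.5.2".

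On who is in the data, section 9.3 is inclusive: "The Safety Analysis Set will include data from all subjects who receive any amount of study drug".

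The trigger equates one cycle with 28 days. The Synopsis, the Schedule of Activities and section 4.5 use 21-day cycles.

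**The concern.** A safety review with an enrolment hold should come no later when patients are being lost early. Here the count rests on those who lasted a full cycle. A death or a toxicity stop in cycle 1 adds a patient to the exposed group but not to the count, so accrual continues while the trigger stands still.

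Other parts of the plan treat early losses differently. In section 4.3, patients who miss the dosing threshold are non-evaluable only when the reason is something other than a DLT. In section 9.3, the ORR analysis keeps patients who died or stopped early for toxicity or clinical progression. The 9.5.2 trigger has no matching provision.

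What is at stake is how many patients are exposed before the one compulsory pause. The question is a live one: section 2.3.1 reports more marrow toxicity than expected when olaparib is combined with chemotherapy, and section 4.5 says published data on this continuous schedule are not yet available.

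**Working it through.** **Inputs.** Trigger: 15 patients with a full cycle (9.5.2). DLT rule: the starting dose passes with at most 1 DLT in 6 (4.2). Cycle-1 loss q, the share of treated patients who leave during cycle 1 for any cause, is not in the documents and is an assumption shown over a range. The plan gives no operating figure for this trigger, so there is none to reproduce.

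**Step 1: number treated when the trigger fires.** If patients are lost independently with probability q, the number treated N when the 15th full-cycle patient is reached is 15 plus a negative binomial count of losses, and its mean is 15/(1 − q). N is at least 20 exactly when 5 or more of the first 19 are lost, so P(N ≥ 20) = P(Bin(19, q) ≥ 5).

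| Assumed q | Mean N | 90th percentile | P(N ≥ 20) |
|---|---|---|---|
| 0% | 15/1.00 = 15.0 | 15 | 0 |
| 5% | 15/0.95 = 15.8 | 17 | .002 |
| 10% | 15/0.90 = 16.7 | 18 | .04 |
| 20% | 15/0.80 = 18.8 | 22 | .33 |
| 30% | 15/0.70 = 21.4 | 25 | .72 |

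Patients still inside cycle 1 when the count is reached come on top of these numbers, whichever way the trigger is worded.

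**Step 2: allow for the DLT rule.** Assume, as the case most favourable to the plan, that every cycle-1 loss is a DLT and that no other DLTs occur. The starting dose then passes with probability (1 − q)^6 + 6q(1 − q)^5:

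- q = 20%: 0.2621 + 0.3932 = 0.655
- q = 30%: 0.1176 + 0.3025 = 0.420

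With 0 losses in the first 6, N ≥ 20 needs at least 5 losses in the next 13. With 1 loss in the first 6, it needs at least 4. So P(N ≥ 20 | pass) is:

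- q = 20%: (0.2621 × 0.0991 + 0.3932 × 0.2527) / 0.6554 = 0.1253 / 0.6554 = .19
- q = 30%: (0.1176 × 0.3457 + 0.3025 × 0.5794) / 0.4202 = 0.2160 / 0.4202 = .51

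The chance of both passing and reaching 20 at the starting dose is the numerator: .13 and .22.

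**Step 3: the reworded trigger.** If a patient counts on completing cycle 1 or on stopping during it, the review falls when 15 treated patients are accounted for, at every q.

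**The case against.** The strongest reply is that cycle-1 toxicity already has its own control. The DLT rule acts at six patients rather than 15, covers most related Grade 3 or higher events in cycle 1, and forces a dose reduction automatically. This stands, and Step 2 shows how much it takes off. It does not close the gap: at an assumed 20% or 30% the starting dose still passes with probability .66 or .42. At TMZ 50 mg/m² the rule no longer applies, and section 4.2 hands safety to 9.5.2.

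Second, other oversight continues. SAEs are reported within 24 hours (8.4.1), and the DSMC sees AEs and SAEs at least every six months. On the Synopsis dates (January 2020 to January 2022), even accrual of 30 patients over 24 months is 1.25 a month, so 15 patients take about 12 months and at least one periodic review should come first. This stands too, but suspension after a periodic review is discretionary.

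Third, nothing in the documents supports a loss of 20% to 30%. Entry requires ECOG 0–1 and a life expectancy of at least 16 weeks, and section 8.4.5 manages toxicity by interruption and dose reduction. At 10% or less the delay is one or two patients on average. This is correct.

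Fourth, wanting a full cycle of exposure before the review is a legitimate aim. It is, but it does not require early stoppers to be left out of the count.

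A reader might also infer three stronger things that the documents do not support:

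- **That the review comes later the more toxic the regimen is.** Only loss within cycle 1 moves the trigger. Toxicity that is managed or arises later does not, while early progression or withdrawal does.
- **That early deaths and stops are hidden from the DSMC.** They are in the Safety Analysis Set and in the reports the DSMC receives.
- **That the replacement rule in section 9.2 causes the delay.** That rule ("Patients that are not evaluable may be replaced to ensure the appropriate number of evaluable patients is enrolled") concerns evaluability for response. With 30 patients planned, accrual passes 15 with or without it. It would matter only if more than 30 were treated before the review, a chance of 0.6% at q = 30%.

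**Conclusion.** The point holds in a limited form. Followed as written, the only DSMC review with a built-in enrolment hold is delayed by every patient lost during cycle 1, and the direction never reverses. The size depends wholly on an assumed loss rate: about one extra patient on average at 5%, two at 10%, four at 20% and six at 30%, before allowing for the DLT rule. With that rule, and if every early stop were a DLT, the chance that at least 20 are treated first, given that the starting dose passes, is .19 at 20% and .51 at 30%. If early losses are mostly progression or withdrawal, the DLT rule does not reduce these chances, but the loss is then not a toxicity signal.

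The conclusion also rests on reading the trigger as a full cycle received. The stated number of days favours that reading, though the sentence does not use the word completed. The finding is the same whether the cycle is taken as 21 or 28 days; the longer reading would also leave out patients who stop in days 22–28. Given the other safeguards, this is a cheap improvement worth making rather than a failure of safety oversight.

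**What to change.** Reword the trigger in section 9.5.2: the DSMC performs the interim safety analysis, and enrolment is suspended pending its approval, once 15 treated patients have each either completed cycle 1 or stopped treatment during it for any reason, including death. State that all treated patients (the Safety Analysis Set) are included in that review. In the same edit, reconcile the 28 days given for one cycle with the 21-day cycle used elsewhere.

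The cost is one sentence. Sample size, the Simon two-stage rule and dosing are unchanged. The downside is that some of the 15 may contribute less than a full cycle of exposure.
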